Surgical procedure or Specimen removal during surgery				
Tissue banking (complete Section 12)				
Use of pre-existing tissues/specimens				
Other (list):				

- **Standard of care procedures are procedures performed in the course of normal medical care.*
- ***Research Procedures are performed for the purposes of this research alone.*

13. Please describe the research design and all study related procedures.

- Describe ALL PROCEDURES ASSOCIATED WITH THIS RESEARCH. This includes standard of care and research procedures.
- For complex studies please include diagrams and tables. Be sure to describe when each procedure will be performed. Be sure to provide information for each cohort, including normal controls.

Study participants based on the inclusion and exclusion criteria listed below will be recruited from the Oncology clinics and medical services of the Cleveland VA. The study oncologist will review the study with them. Subjects that consent will be randomized to one of the two arms, vaccine or no vaccine. Individuals will undergo blood draws for immunologic assays according to time points depicted in the figure below. Each blood draw (25 ml each) has been timed to follow routine clinical monitoring as ordered by the oncologist for maximum feasibility.

- The first blood draw will be at the time of consent into the study. We anticipate this time to be the first visit with the oncologist. They will receive ZOSTAVAX on that day if they are in that arm of the study.
- The second blood draw will be on the day of chemotherapy initiation, no earlier than 14 days post-vaccination. This will be longer than 14 days for example when there is surgery between the vaccination and the start of chemotherapy.
- The third blood draw will be at the start of the second chemotherapy cycle.
- The fourth blood draw will be 3-24 months post chemotherapy cessation. The timing of the final blood draw is based on cessation of chemotherapy and not any concurrent radiation therapy that would be also completed by the 3-6 month post-chemotherapy sampling.

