The subjects chemotherapy is decided by the Oncologist and/or Tumor Board in consultation. The duration of chemo similarly is also decided clinically. If the patient needs surgery or XRT

as part of the therapy, it is decided on entirely by the clinicians. The study is working around all of these clinical decisions.

Subjects will be called between visit 2 and 3 and then between visits 3 and 4. They will be asked if they had a side effects or event that may have been serious since the last study visit or telephone contact. They will also be asked if they were exposed to anyone who has chickenpox or shingles, and if they had any symptoms of shingles.

For 4 weeks after they receive their shot, they will be asked to record information about potential vaccine side effects on the vaccination Report Card.

14. Will the research involve the following?

N/A Chart/Data Review

Placebo Group No Yes (describe):

Other Control Group No Yes (describe): The control group is persons that do not get the vaccine.

Randomization No Yes (describe): We will obtain clinical information to determine eligibility this includes meds and PMH and then follow the subject's clinical course to know when to do the subsequent sampling. We will use a cloud based randomized tool to generate the list before the start for the whole study for what the order of vaccine or no vaccine will be. We will then have paperwork packets in the order of enrollment premade. We will open each packet at the consenting time and find vaccine or not and enroll and begin the study.

Deception No Yes (describe):

15. Does the research involve the use and/or disclosure of Individually Identifiable Health Information in any form or medium?

No Yes If yes, complete the required HIPAA Waiver/Authorization forms.

16. Does the study include the administration of a study agent that does not require FDA approval and does not require an IND (e.g. vitamins, food supplements, isotope tracers, alternative medicines, etc.)?

No Yes -provide a detailed description of the procedures used to assure patient safety:

17. Will radioactive material be administered or will subjects be exposed to ionizing radiation?

• Ex. Radiographic equipment, fluoroscopic equipment, and CT scanners, etc.

No Yes

18. In your judgment, could the objectives of the research be met in a way that presents less risk to subjects?

No Yes please explain:

Section 4 – Subject Selection, Recruitment, and Vulnerable Populations

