 - History of anaphylactic/anaphylactoid reaction to gelatin, neomycin, or any other component of the vaccine.

N/A Chart/data review

31. By role, (PI, Coordinator, etc.) who will assess for eligibility and how will this be accomplished?

PI, Co-I and/or Coordinator after we have a waiver exemption will prereview subjects in CPRS to determine eligibility. We will examine the medical issues for inclusion and exclusion. We will also look for any discussion or diagnosis that showed or suggested lack of capacity to consent as we will only enroll those that can consent for themselves.

32. Are any subjects excluded on the basis of race, ethnic group, understanding of English, socioeconomic status, education, gender, or pregnancy?

- *Note: It is appropriate to indicate that you do not anticipate encountering potential subjects who do not speak English based on the population to be studied*

No **Yes - (provide justification):** If a subject does not speak English we do not feel we can consent them properly and follow them for adverse reactions to the vaccine for example.

N/A Chart/data review

33. Will subjects be reimbursed or paid an incentive for participating?

No (skip to item #35) **Yes**
 N/A Chart/data review (skip to item #38)

34. How and when will they be paid?

Cash **Check** **Other** -please explain: VISA card will be used if we are not able to work out a mechanism for cash with the VA Foundation. [name] had a discussion with [name] from the VA Research Foundation on 7-11-14 regarding this topic. [name] is not aware of a way they can do cash at this moment. It be an option in the future and we could then use this rather than a preloaded VISA.

Prorated -provide schedule: \$20 per blood draw and \$20 additional for travel costs for the final blood draw if it does not correspond with a routine visit for care that is already scheduled.
Fixed -provide schedule

35. Will subjects be responsible for any of the costs related to the research?

No **Yes- please explain:**

36. Will treating physicians, clinicians, or researchers be compensated or paid an incentive for referring or enrolling subjects?

No **Yes -please explain:**

37. Please describe steps you will take to ensure that subject selection is fair and equitable:

We have very objective exclusion criteria so that should allow for fair recruiting.

Section 5 – Risks and Benefits

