persons in particular already have evaluations on the chart discussing capacity. It is not feasible for us to send all subjects for a capacity evaluation and still meet the strict time parameters of 14 days between vaccination and treatment.

47. Will anyone other than the subject be authorized to provide consent or permission for the subject's involvement in the research?

- *e.g., parents, court ordered guardian, spouse, etc.*

No Yes -please explain:

48. Describe how and where informed consent will be obtained:

Consent will be obtained in the VA exam room or hospital room of the subject. The subject will be given the consent and have time to read it. They will also have the study explained and allow time for the study staff to answer questions. The research team will then question the subject about the key elements of the study to assure they understand it.

49. Will there be an opportunity for potential subject to take the consent form home to discuss participation and options with family members?

Yes No - please explain:

It is not possible to take the consent home in virtually all cases as the subject will not have sufficient time to fit into the 2 week time window between the shot and chemotherapy if they take the consent home.

50. List by role who will be obtaining informed consent from subjects or their legally authorized representatives:

- *ex. study coordinator, co-investigator, research nurse, research assistant, PI*

All members of the study team are authorized to obtain consent.

51. Please describe how informed consent will be obtained from subjects who do not read or understand English;

- *identify any languages likely to be encountered, and attach a copy of a translated and authenticated informed consent document*
- *It is appropriate to indicate that you do not anticipate encountering potential subjects who do not speak English based on the population to be studied*

We will exclude those that do not understand English. If they cannot read we can read the whole consent to them.

52. Describe who (by Role ex. PI, Coordinator, etc.) and how it will be determined that subjects and/or legally authorized representative understand the research and their rights.

- *ex. question and answer, repeat back parts of the research, describe a procedure...etc*

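### The protocol does not require enrolment to be complete before the allocation packet is opened and describes no concealment, so arm-dependent enrolment is not ruled out

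*Protocol*

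**What the plan says.** Protocol Section 3, item 14 is the only place that sets out how allocation works. On the sequence: "We will use a cloud based randomized tool to generate the list before the start for the whole study". On how it is held: "We will then have paperwork packets in the order of enrollment premade". On its use: "We will open each packet at the consenting time and find vaccine or not and enroll and begin the study". The same item defines the comparator: "The control group is persons that do not get the vaccine". No placebo or blinding is described.

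Item 13 of the same section gives the order differently: "Subjects that consent will be randomized to one of the two arms, vaccine or no vaccine". It places the first blood draw at consent and says of the vaccine: "They will receive ZOSTAVAX on that day if they are in that arm of the study". Consent, reveal and vaccination can therefore all fall within one visit.

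On who recruits, Section 6, item 50 says: "All members of the study team are authorized to obtain consent". On eligibility, item 14 begins by stating that clinical information will be gathered to settle it. Section 4, item 31 adds that the PI, a co-investigator and/or the coordinator "will prereview subjects in CPRS to determine eligibility".

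The documents do not say whether packets are sealed or opaque, who holds them or the list, whether openings are logged, or how a subject who leaves after the opening is counted. SAP section 2.7, the only SAP text available, does not describe randomisation and defines no all-randomised analysis set.

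**The concern.** Random allocation protects the comparison only if nobody can act on the assignment before the subject is irrevocably in the trial. If the arm is visible while enrolment is still open, a subject can be deferred, judged unsuitable or allowed to decline because of it. The two arms may then differ in ways that randomisation was meant to prevent.

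Several features of this trial could make the arm matter at that moment:

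- The vaccine arm needs at least 14 days before therapy starts (Section 3, item 13; Section 4, item 30). Section 6, items 46 and 49 describe that window as tight.
- A control subject has a reason to walk away, because the vaccine can be obtained later from the primary provider (Section 5, item 41).
- Some entry criteria in item 30 call for judgement, such as the expected end of chemotherapy and whether palliative treatment is open-ended.
- The oncology co-investigators are also the subjects' treating physicians (Section 7, item 54).

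The primary measure, fold change from the subject's own day-0 ELISPOT count, adjusts for baseline level. It does not adjust for a difference between arms in the capacity to respond. Pilot status does not remove the concern, because the data are meant to inform the sample size of a larger study.

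**Working it through.** **Step 1: the order of events, side by side.**

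| Event | Item 13 | Item 14 |
|---|---|---|
| Signed consent | Before randomisation | Same occasion as the opening; which comes first is not stated |
| Eligibility | Not placed relative to the opening | Information gathered first; no final confirmation required before opening |
| Enrolment or log entry | Not mentioned as a step | Written after the arm is found |
| Day-0 blood | At consent; not placed relative to the opening | Not mentioned |
| Packet opened | Not mentioned | At consent, before enrolment as written |

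The two items can be reconciled if the opening follows the signature and if enrolling means starting study procedures. They conflict if item 14 is a strict sequence. Neither item makes confirmed eligibility and a log entry a condition for opening.

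**Step 2: concealment.** Ordered packets opened one per subject limit which assignment a given subject can receive, and that is a partial safeguard. It works only if the next packet cannot be read in advance. Sealing, opacity, custody and an opening log are all unstated.

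**Step 3: the plan's own figures** (Protocol item 11; SAP section 2.7).

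- Attrition: 90 x 0.85 = 76.5, which agrees with the stated 76.
- t-test, 38 per arm: df = 2 x 38 - 2 = 74, noncentrality = d x sqrt(38/2) = 4.36d. Power of 0.80 at alpha 0.05 is reached at d = 0.576 one-sided and d = 0.651 two-sided. The stated 0.58 therefore reproduces as a one-sided test. Sidedness is not stated, which is a separate matter.
- 2 x 3 repeated measures, between-group effect, assumed correlation 0.5: lambda = f^2 x 76 x 3/(1 + 2 x 0.5). The detectable f is 0.266, which agrees with the stated 0.27.

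None of these figures depends on when the packet is opened.

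**Step 4: an illustration of size.** The inputs are assumptions, not values from the documents. Let q be the share of one arm enrolled selectively and D the difference in mean outcome of those subjects, in SD. The shift in the arm difference is q x D. The last column is the two-sided rejection rate of a t-test with 38 per arm when the vaccine has no effect, from the noncentral t with noncentrality 4.36 x q x D.

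| q | D | Shift (SD) | Share of 0.58 | Rejection rate |
|---|---|---|---|---|
| 0.05 | 0.5 | 0.025 | 4% | 5.1% |
| 0.10 | 0.5 | 0.05 | 9% | 5.5% |
| 0.10 or 0.20 | 1.0 or 0.5 | 0.10 | 17% | 7.1% |
| 0.20 | 1.0 | 0.20 | 34% | 13.8% |

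The table assumes that all steering runs in one direction. It uses a t-test at a single time point, whereas the initial overall analysis is the 2 x 3 repeated-measures ANOVA.

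**The case against.** The strongest reply is that item 14 is informal form-filling prose, not a strict sequence. Item 13 puts consent before randomisation and treats consent as entry into the study. Opening the packet just after the signature, at the same visit, is acceptable practice. Eligibility is reviewed in the chart beforehand, and Section 4, item 37 describes the exclusion criteria as objective. The SAP text available starts at section 2.7, so procedural detail may sit in parts that cannot be seen.

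Much of this stands, and it rules out three stronger readings that a reader might infer:

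- That the arm is in fact known before enrolment. The text permits this but does not establish it, because item 13 supports the opposite order.
- That subjects lost after the reveal would go uncounted. The documents are silent on this. If consent comes first, such a loss would be an ordinary withdrawal after randomisation.
- That item 50 shows recruiters can see the next assignment. It says who may take consent and nothing about access to the packets.

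The reply does not close the gap. A chart review before the visit is not a final confirmation of eligibility made before the opening. The benign reading also leaves the custody and sealing of the packets undescribed.

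**Conclusion.** The point holds as a gap in the allocation procedure that should be closed. Items 13 and 14 leave the order of consent, eligibility, enrolment and opening unclear. No concealment of the ordered packets is described in a trial where the arm is evident once revealed. Arm-dependent enrolment is therefore not ruled out. If it did occur, it would be hard to detect or correct afterwards.

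The documents give no basis for a size. The 0.05-0.20 SD range (10-20% steered) is illustrative only. A reader might take the 13.8% rejection rate as the trial's expected false-positive rate. The documents do not support that: it needs both assumed inputs at their upper ends and every steered subject moved the same way, and nothing in the plan shows that patient selection shifts fold change by that much.

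**What to change.** Rewrite item 14, and align item 13 with it, so that the order is explicit:

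1. Consent is signed and eligibility is confirmed.
2. The subject is logged as enrolled with a study number, and the day-0 blood is drawn. Every randomised subject then has a sample for the fold-change denominator.
3. Only then is the next sequentially numbered, sealed, opaque packet opened, and the opening is logged.

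Name a holder of the list and the unopened packets who does not recruit. Because item 50 lets every team member take consent, that person must be excluded from doing so. The research pharmacy, which already stores the vaccine (Section 9, item 72), or the study statistician could serve. Alternatively, the cloud tool could release each assignment at step 3, if it can do so; the protocol says only that it generates a list. State in the SAP that every subject whose packet is opened counts as randomised.

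The cost is one reworded paragraph, one SAP sentence and a small logistical step at the consent visit. Sample size, power and alpha do not change. If the team already works this way, the rewrite only documents it.

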30 ZOSTAVAX

30 no vaccine

21. Estimated number of subjects to be studied or charts/records to be reviewed at all sites

- Provide answers for each cohort including normal controls; (patients, family members, treating physicians,)

30 ZOSTAVAX

30 no vaccine

The Duke University site will have 15-ZOSTAVOX and 15 no vaccine

N/A SINGLE SITE

22. Duration of individual subject participation

Provide answers for each cohort including normal controls; (patients, family members, treating physicians,). 5 years or less depending on the duration of their chemo.

Chart/record review N/A

23. Age range of subjects

- provide answers for each cohort, including normal controls:

Adults 18 years or greater

Specific age range (list age range): 50 years and older for both cohorts

Children –waiver from VACO: attached pending- provide submission date:

**Contact AO/Research [contact] for guidance..

24. Which of the following will be recruited or reviewed for this study (check all that apply)?

Veteran Inpatients

Men

Veteran Outpatients

Women

Veteran Families

*Normal volunteers

*Non-Veterans; Provide justification

*According to VHA Handbook 1605.04 Notice of Privacy Practices VHA must provide a copy of its VHA Notice of Privacy Practices to all non-Veteran patients (e.g., active duty personnel or those seeking care in humanitarian circumstances) receiving care or treatment at a VHA health care facility or non-Veteran research subjects enrolled in an approved VHA research study with clinical trials. VA Form 10-0483 Acknowledgement of the Notice of Privacy Practices should be signed by the non-Veteran research subject at the time of consent and given a copy of the Notice of Privacy Practices. Once the Acknowledgement Form is signed please send a copy to the Privacy Officer. If additional information is needed please contact your Facility Privacy Officers [name] or [name] [contact] / [contact] [contact] / [contact].

25. Which vulnerable population(s) will be TARGETED for recruitment in this study:

- Indicate only those populations that are specifically targeted for the research described in this document.
- *It is not necessary to check any box if, for example, your study will include a full range of subjects, some of whom may be elderly or subjects who might incidentally be employees.*

- N/A Chart Review (proceed to Item 30)
- NONE (proceed to Item 26)
- Medical students, house staff, or Employees of the VAMC or Case
- Pregnant Women OR Women who are Breastfeeding, Human Fetuses, or Neonates
- Children – Complete Section 14 “Children as Research Subjects”
- Prisoners (The LSCDVAMC does not conduct research involving prisoners)
- Targeting Persons over Age 65
- Persons with Acute/Severe Mental/Physical Disabilities (describe):
- Persons with Cognitive, Social, Economic, or Educational Disadvantages (describe):
- Others (describe):

a. Provide the Scientific and Ethical reasons for Targeting these vulnerable populations in the research:

b. What additional safeguards or provisions will be used to protect the rights and welfare of the identified targeted vulnerable subjects?

- Surrogate consent
- Subject assent
- Use of a consent or Medical monitor
- Use of a waiting period
- A patient advocate will participate in the informed consent process
- Key elements of informed consent will be presented orally
- No supervisor or rater will be involved in obtaining consent

Other - Describe Additional safeguards you plan to use:

c. Describe the procedures used to ensure that the subject's legally authorized representative is well informed regarding his/her role and obligation to protect persons with impaired decision making capacity:

26. Procedures for Recruiting Subjects -check all that apply and attach all recruitment materials:

Not Applicable

Materials; Recruitment Letter, Posting on Bulletin Board, Brochure, Flyer, Post card, etc.

Media; Internet Ads, Press Releases, Newspaper, Radio

Investigator's Patient Population

Physician Referral

Letters to Physicians/Clinicians

Other (describe):

27. Will VA computer systems be used to identify potential subjects?

- e.g. VISTA, CPRS, Pharmacy Databases, other clinical databases, etc.

No Yes- Describe how the computer will be used to identify patients. List all systems used and all information to be collected: We will request a HIPAA waiver so our coordinator can help the oncology staff identify potential candidates for the study. We will review the charts of the future clinics and inpatients anticipating chemo in CPRS to do a prescreen of subjects for eligibility to the study. This information will then be communicated to the study oncology providers prior to their clinic appointment or inpatient discharge.

28. Will subjects be identified and/or recruited in clinics and/or inpatient wards at the LSCDVAMC?

No Yes- explicitly describe your process for identifying and/or recruiting these patients: (address all cohorts): See the answer for question 27. We will focus on subjects with recent cancer diagnosis that will be seen in the clinics of oncology or by their inpatient team. We can assist the oncologists in prescreening for suitability to the study. Also the coordinator and Co-I may discuss with the medical teams about our study that we are searching for subjects with oncology diagnosis that will receive chemo soon and the primary providers then may refer subjects to us to screen.

29. In addition to the consent form will any other materials be given to the subject?

N/A Chart/data review

No Yes- check all that apply and submit for IRB review:

Letter

Information Sheets

Questionnaire, Survey, Diary

Other (flyer, brochure, describe): If they enroll they will fill out the vaccine report card.

30. Please list by bullet point inclusion/exclusion criteria for the study.

- *Entry criteria should be as detailed as necessary to define the subject population(s) under study and reduce confounding design. Include precise criteria for age, gender, and other relevant factors.*
- *List specific exclusion criteria which could interfere with the study design or place a subject at risk during the study.*
- *Provide answers for each cohort, including normal controls.*

Inclusion criteria:

- Solid organ tumor patients that have at least 14 days between entry into the study with ZOSTAVAX vaccination and initial therapy for their malignancy that will include chemotherapy alone or surgery with subsequent chemotherapy plus or minus radiation therapy.
- A plan for chemotherapy that at the onset at least has an anticipated stop date within 3-6 months of our sample collection phase of the study.
- Age 50 or older

Exclusion criteria:

- Prior history of HZ or shingles vaccine
- Systemic chemotherapy <3 months prior to enrollment
- Any history of hematologic malignancy, HIV/AIDS, hematopoietic stem cell transplant, or other cellular immunodeficiency state
- Those receiving immunomodulating drugs at the time of vaccination such as prednisone, methotrexate, azathioprine, mercaptopurine, or other biologics including TNF- α inhibitors
- Widespread metastatic tumor with bone marrow involvement
- Indefinite duration palliative chemotherapy subjects
 - Inability to communicate with the study staff or being unable to consent for themselves.
 - History of anaphylactic/anaphylactoid reaction to gelatin, neomycin, or any other component of the vaccine.

N/A Chart/data review

31. By role, (PI, Coordinator, etc.) who will assess for eligibility and how will this be accomplished?

PI, Co-I and/or Coordinator after we have a waiver exemption will prereview subjects in CPRS to determine eligibility. We will examine the medical issues for inclusion and exclusion. We will also look for any discussion or diagnosis that showed or suggested lack of capacity to consent as we will only enroll those that can consent for themselves.

32. Are any subjects excluded on the basis of race, ethnic group, understanding of English, socioeconomic status, education, gender, or pregnancy?

- *Note: It is appropriate to indicate that you do not anticipate encountering potential subjects who do not speak English based on the population to be studied*

No **Yes - (provide justification):** If a subject does not speak English we do not feel we can consent them properly and follow them for adverse reactions to the vaccine for example.

N/A Chart/data review

33. Will subjects be reimbursed or paid an incentive for participating?

No (skip to item #35) **Yes**
 N/A Chart/data review (skip to item #38)

34. How and when will they be paid?

Cash **Check** **Other** -please explain: VISA card will be used if we are not able to work out a mechanism for cash with the VA Foundation. [name] had a discussion with [name] from the VA Research Foundation on 7-11-14 regarding this topic. [name] is not aware of a way they can do cash at this moment. It be an option in the future and we could then use this rather than a preloaded VISA.

Prorated -provide schedule: \$20 per blood draw and \$20 additional for travel costs for the final blood draw if it does not correspond with a routine visit for care that is already scheduled.
Fixed -provide schedule

35. Will subjects be responsible for any of the costs related to the research?

No **Yes- please explain:**

36. Will treating physicians, clinicians, or researchers be compensated or paid an incentive for referring or enrolling subjects?

No **Yes -please explain:**

37. Please describe steps you will take to ensure that subject selection is fair and equitable:

We have very objective exclusion criteria so that should allow for fair recruiting.

Section 5 – Risks and Benefits

38. Please list by bullet and describe the reasonably foreseeable physical, psychological, social, economic, and privacy risks, side effects, or discomforts associated with the research and their expected frequency and severity.

- *If this study is a retrospective chart review, or involves only the analysis of data, risk may still be present in the form of data security concerns.*

Some reported risks of ZOSTAVAX include:

- o Injection site reactions such as: local redness, swelling, pain and tenderness, itching, bruising, and warmth.
- o Headache
- o Fever
- o Allergic reaction, which may be life-threatening

- o Rash, which may resemble chickenpox
- o Swollen glands near the injection site (may last a few days to a few weeks)
- o Joint pain
- o Muscle pain

These reactions are either rare or mild in severity making this a safe vaccine with very few exclusions by the FDA.

Blood samples: drawing blood from your arm may cause pain, bruising, lightheadedness, and rarely, fainting or infection.

Loss of privacy is always a risk with any study. We are not collecting those most sensitive topics of information and we will code the sample as soon as they are enrolled so these risks are minimal.

